5.6 Adverse Events (AE) and Serious Adverse Events (SAE)

This study will be conducted in compliance with the Data Safety Monitoring Plan (DSMP) of the Robert H. Lurie Comprehensive Cancer Center of Northwestern University. The level of risk attributed to this study requires moderate intensity monitoring, as outlined in the [DSMP](#). All SAEs will be reported in real time to Northwestern University's Quality Assurance (QA) Dept. and the Northwestern IRB. All AEs that are possibly, probably, or definitely related to the intervention will be reported to Northwestern University's QA Dept. on a semi-annual basis. In addition, the study will abide by all safety reporting regulations, as set forth in the Code of Federal Regulations.

5.6.1 Adverse Event Monitoring & Reporting

Adverse event data collection and reporting, which are required as part of every clinical trial, are done to ensure the safety of subjects enrolled in the studies as well as those who will enroll in future studies using similar agents. Adverse events are reported in a routine manner at scheduled times during a trial (see Sections 5.2 and 5.3 for time points). In addition, certain adverse events must be reported in an expedited manner to allow for optimal monitoring and patient safety and care.

5.6.2 Definitions & Descriptions

5.6.2.1 Adverse Events

An adverse event (AE) is any untoward medical occurrence in a patient receiving study treatment and which does not necessarily have a causal relationship with this treatment. An AE can therefore be any unfavorable and unintended sign (including an abnormal laboratory finding), symptom, or disease temporally associated with the use of an experimental intervention, whether or not related to the intervention.

Recording of AEs should be done in a concise manner using standard, acceptable medical terms. In general, AEs are not procedures or measurements, but should reflect the reason for the procedure or the diagnosis based on the abnormal measurement. Preexisting conditions that worsen in severity or

STU#:00208657

Version 3.1

11/25/2019

frequency during the study should also be recorded (a preexisting condition that does not worsen is not an AE). Further, a procedure or surgery is not an AE; rather, the event leading to the procedure or surgery is considered an AE.

If a specific medical diagnosis has been made, that diagnosis or syndrome should be recorded as the AE whenever possible. However, a complete description of the signs, symptoms and investigations which led to the diagnosis should be provided. For example, if clinically significant elevations of liver function tests are known to be secondary to hepatitis, "hepatitis" and not "elevated liver function tests" should be recorded. If the cause is not known, the abnormal test or finding should be recorded as an AE, using appropriate medical terminology (e/g/ thrombocytopenia, peripheral edema, QT prolongation).

For this study, only AEs that are possibly, probably, or definitely related to the intervention will be collected (Refer to Section 5.6.2.3 for separate criteria for collection of SAEs). Expected symptoms are listed in Sections 5.2 and 5.5 and/or can be found in the U.S. FDA drug package insert. AEs that are possibly, probably, or definitely related to the intervention will be collected from the time of signing informed consent until 30 days after receipt of the intervention at the 1 month follow-up time point. Refer to Sections 5.2 and 5.3 for additional information on the time points for AE collection.

5.6.2.2 Severity of Adverse Events

All adverse events will be graded according to the NCI Common Terminology Criteria for Adverse Events (CTCAE) version 5.0. The CTCAE v5.0 is available at https://ctep.cancer.gov/protocoldevelopment/electronic_applications/ctc.htm

If no CTCAE grading is available, the severity of an AE is graded as follows:

- Mild (grade 1): the event causes discomfort without disruption of normal daily activities.
- Moderate (grade 2): the event causes discomfort that affects normal daily activities.
- Severe (grade 3): the event makes the patient unable to perform normal daily activities or significantly affects his/her clinical status.
- Life-threatening (grade 4): the patient was at risk of death at the time of the event.
- Fatal (grade 5): the event caused death.

STU#:00208657
Version 3.1
11/25/2019

5.6.2.3 Serious Adverse Events

All serious adverse events (SAEs), regardless of expectedness and attribution, occurring from the time of signed informed consent, through 30 days after the last administration of study drug (i.e. at the 1 month follow-up time point), must be reported upon discovery or occurrence.

An SAE is defined in regulatory terminology as any untoward medical occurrence that:

- **Results in death.**
- **Is life-threatening.**
The patient was at risk of death at the time of the event; it does not refer to an event that hypothetically might have caused death if it were more severe.
- **Requires *in-patient hospitalization or prolongation of existing hospitalization for ≥ 24 hours.***
- Results in *persistent or significant disability or incapacity.*
- Is a *congenital anomaly/birth defect.*
- Is an *important medical event.*

Any event that does not meet the above criteria, but that in the judgment of the investigator jeopardizes the patient, may be considered for reporting as a serious adverse event. The event may require medical or surgical intervention to prevent one of the outcomes listed in the definition of "Serious Adverse Event". For example: allergic bronchospasm requiring intensive treatment in an emergency room or at home; convulsions that may not result in hospitalization; development of drug abuse or drug dependency.

5.6.2.4 Unanticipated Problems Involving Risks to Subjects or Others (UPIRSO)

A UPIRSO is a type of SAE that includes events that meet ALL of the following criteria:

- Is *unanticipated* in terms of nature, severity, or frequency
- Places the research subject or others at a different or *greater risk of harm*
- Is deemed to be *at least possibly related* to participation in the study.

5.6.2.5 Expedited Reporting to Northwestern University's QAM/DMC

All SAEs must be reported to the assigned QAM within 24 hours of becoming aware of the event. Completion of the NU CRO SAE Form, provided as a separate document, is required.

The completed form should assess whether or not the event qualifies as a UPIRSO. The report should also include:

- Protocol description and number(s)
- The patient's identification number

STU#:00208657

Version 3.1

11/25/2019

- A description of the event, severity, treatment, and outcome (if known)
- Supportive laboratory results and diagnostics
- The hospital discharge summary (if available/applicable)

All SAEs will be reported to and reviewed by the DMC at their next meeting.

5.6.2.6 Expedited Reporting to Northwestern University's IRB

- Any death of an NU subject that is unanticipated in nature and at least possibly related to study participation will be promptly reported to the NU IRB within 24 hours of notification.
- Any death of an NU subject that is actively on study treatment (regardless of whether or not the event is possibly related to study treatment)
- Any death of a non-NU subject that is unanticipated and at least possibly related and any other UPIRSOs will be reported to the NU IRB within 5 working days of notification.
- All other deaths of NU subjects not previously reported, other non-NU subject deaths that were unanticipated and unrelated, and any other SAEs that were not previously reported as UPIRSOs will be reported to the NU IRB at the time of annual continuing review.

5.6.2.7 Routine Reporting to Northwestern University's QAM/DMC

All routine AEs (those that are possibly, probably, or definitely related to the intervention) must be reported to the assigned QAM on a semi-annual basis.

6.0 DATA AND SPECIMEN BANKING

NA

7.0 SHARING RESULTS WITH PARTICIPANTS

Specific or detailed study results will not be shared with the study participants

8.0 STUDY TIMELINES

IRB submission and approval process 1 month

Recruitment 6 months

Participant follow-up 6 months

Statistical analysis and Manuscript development 2 months

Duration of participation for each subject is approximately 6.5 months

STU#:00208657

Version 3.1

11/25/2019

9.0 INCLUSION AND EXCLUSION CRITERIA

Inclusion criteria:

1. Men with prostate cancer (with or without metastatic disease) on ADT for at least 2 months
2. Must have greater than 28 hot flashes per week
3. Age \geq 18 years and less than \leq 70 years
4. Body Mass Index (BMI) less than 32
5. Willingness to undergo image guided intervention
6. Must have the ability to understand and the willingness to sign a written informed consent prior to registration on study

Exclusion criteria:

1. Conditions that preclude SGB or sham intervention (e.g., anatomic abnormalities of the anterior neck or cervical spine; metastatic disease in or near the cervical spine; goiter; cardiac/pulmonary compromise; sleep apnea; acute illness/infection; coagulopathy or history of bleeding disorder; allergic reactions/contraindications to a local anesthetic or contrast dye)
2. Current treatment of prostate cancer with radium or chemotherapy at the time of registration, or within \leq 14 days prior to the date of SGB intervention.
3. Use of treatments in the past two months that can affect HF (e.g., testosterone or androgen supplementation)
Note: SSRIs, serotonin norepinephrine uptake inhibitors, and membrane stabilizers will be allowed but must be on stable unchanged dose for at least 8 weeks prior to registration.
4. Inability to write, speak, or read in English
5. Any other illness or condition that the treating investigator feels would interfere with study compliance or would compromise the patient's safety or study endpoints

10.0 VULNERABLE POPULATIONS

NA

11.0 PARTICIPANT POPULATION

Accrual Number:	Category/Group: Adults	Consented: Maximum Number to be Consented or Reviewed/Collected/Screened	Enrolled: Number to Complete the Study or Needed to Address the Research Question
Total:	18	18	14

STU#:00208657

Version 3.1

11/25/2019

12.0 RECRUITMENT METHODS & REGISTRATION

12.1 Recruitment Methods

Participants will be recruited from [name] practice in addition to other prostate cancer oncologists and caregivers in the NM Division of Hematology & Oncology. Participants will call the study team to go through the 10 minute screening survey. This includes a baseline HFRDIS questionnaire to ensure the patient would qualify. The participant needs to have a score of >40 to be eligible for the study. Once it is determined they meet the criteria for the HFRDIS subjects will be asked to come to the research office for consenting if they are interested in the study.

Flyers will be posted around the NMH medical center to advertise the study.

The trial will be posted on clinical trials.gov

12.2 Registration Procedures

For potential patients for this study, study teams are asked to inform the Quality Assurance Monitor (QAM) of the date and time that the patient will need to be registered ([contact]).

BEFORE a patient can be treated on study, please complete and submit the following items to confirm eligibility and receive a subject identification number:

- Eligibility eCRF (complete in NOTIS at <https://notis.fsm.northwestern.edu>)
- Eligibility checklist (signed and dated by the treating physician – upload in NOTIS)
- Signed and dated informed consent document (upload in NOTIS)

The QAM will review the above registration materials, register the patient, assign an identification number, and send a confirmation of registration to involved personnel. Registration will then be complete and the patient may begin study treatment.

13.0 COMPENSATION FOR PARTICIPATION IN RESEARCH ACTIVITIES

Participants will receive \$100 by check mailed to their address at the completion of the study to compensate for their time and effort in this study. They will receive parking passes for the on-site study visits.

14.0 WITHDRAWAL OF PARTICIPANTS

Patients can be taken off the study treatment and/or the study as a whole at any time at their own request, or they may be withdrawn at the discretion of the investigator for safety, behavioral or administrative reasons. The reason(s) for discontinuation must be clearly documented on the appropriate CRF. An example of when participants may be withdrawn from the research without their consent is if they are non-compliant with providing outcome measures and/or if they begin using a medication known to have an effect on HF. In such cases, or if the participant communicates in writing that he wishes to withdraw, this will be communicated to the study team and the participant and status will be changed from "active" to "inactive".

STU#:00208657

Version 3.1

11/25/2019

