Study Title: Does Stellate Ganglion Blockade (SGB) in Men Treated for Prostate Cancer Improve Hot Flashes? A Pilot Prospective Cohort Study

Study Protocol Version 3.1 11/25 2019

NCT003796195

STU#:00208657

Version 3.1

11/25/2019

PROTOCOL TITLE: Does Stellate Ganglion Blockade (SGB) in Men Treated for Prostate Cancer Improve Hot Flashes? A Pilot Prospective Cohort Study

PRINCIPAL INVESTIGATOR:

[name], MSCI

Department of Anesthesiology

[contact]

[contact]

Co-Investigator

[name], MPH

Department of Medicine, Division of Hematology & Oncology

Statistician

[name]

Department of Anesthesiology

VERSION NUMBER:

3.1

VERSION DATE:

11/25/2019

STUDY SUMMARY:

Special Population(s)	NA
Sample Size	N = 14 is the required number of enrollees who are needed to be evaluable both at baseline and 6 months for the primary outcome. Allowing for dropouts, up to 18 pts might be enrolled
Funding Source	Internal funding
type of consent to be obtained	Written
Site	Single Site
Research Related Radiation Exposure	Yes

STU#:00208657

Version 3.1

11/25/2019

1.0 OBJECTIVES:

Scope: Men with prostate cancer with or without metastatic disease treated with androgen deprivation therapy for at least 2 months, with bothersome refractory hot flashes, will be enrolled as participants in this open label clinical trial.

Aim 1: To determine the effect of stellate ganglion blockade (SGB) for reducing hot flash frequency and severity in men with prostate cancer in the 6 months following the intervention.

Aim 2: To evaluate the effect of SGB on daily hot flash (HF) interference and sleep quality.

Hypotheses: Hot flash frequency, interference and sleep quality will be improved in men following stellate ganglion blockade with local anesthetic.

2.0 BACKGROUND:

Androgen Deprivation Therapy (ADT) is a critical component of advanced prostate cancer treatment but causes numerous adverse effects including decreased bone mass, decreased muscle mass, gynecomastia, erectile dysfunction, loss of sexual desire, depression, disordered sleep, urinary symptoms, and hot flashes (HF)(1). HF are unpleasant paroxysmal episodes of flushing, sweating with vasodilation of the face, neck, and chest. These episodes can last for seconds to minutes and are often associated with night sweats, anxiety, and insomnia and have negative effects on quality of life (9).

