Stellate ganglion blockade (SGB) with local anesthetic may be an effective treatment of HF in men on ADT, but has not been studied in any published clinical trials. The stellate ganglion is a neural structure in the anterior cervical spine region and is part of the sympathetic nervous system. It has been injected safely in the practice of pain management for more than 50 years in cases of post herpetic neuralgia (shingles), complex regional pain syndrome (CRPS) and other painful neuropathies as well as some types of cardiac dysrhythmias. We recently published a prospective, randomized, sham controlled study of SGB in women with natural or surgical menopause, in which we found a 52% decrease in moderate to very severe HF in women who underwent a single SGB with bupivacaine, a local anesthetic, as compared to a 13% decrease in women in the sham control group who underwent an injection of saline. (20).

Another controlled study of SGB in women with breast cancer on endocrine therapy confirmed considerable reductions in frequency and intensity of HF in patients who had SGB (21). Uncontrolled studies of women with breast cancer and heterogeneous populations including postmenopausal women have demonstrated improvements in the frequency and intensity of HF following SGB, with 45-90% reduction in HF frequency or intensity, for durations ranging from 4 weeks to several months (22-24). Together, this literature provides further support of the hypothesis that SGB could be beneficial to men on ADT.

The mechanism of SGB mitigation of HF in men is unclear. The effects of testosterone on prevertebral ganglia are widely variable (25). Anatomic connections between the stellate ganglion and thermoregulatory regions in the brain via third order neurons have been described (26). SGB interrupts the sympathetic nervous system and may modulate norepinephrine levels in these thermoregulatory regions. Androgen deprivation as in ADT appears to change NE levels and activate the sympathetic nervous system in rat models (27), but the detailed interaction between testosterone and NE levels in humans is unclear (25, 28, 29). Some authors have alternatively hypothesized that Nerve Growth Factor (NGF) levels are modulated following SGB (30, 31), and there is evidence that NGF levels may decrease with testosterone withdrawal, affecting neural growth and neural plasticity (32, 33) that could ultimately effect thermoregulation.

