After participants have reviewed and signed the consent form in person, they will be interviewed to determine candidacy for the study. They will be asked to provide information about themselves and their medical history. Participants will consult with [name] who will explain the injection procedure and perform a brief physical examination (focus on cervical range of motion and anterior cervical anatomy) to confirm patient eligibility for the

[name], MD STU00208657

V 3.1 11/25/2019

STU#:00208657

Version 3.1

11/25/2019

study. The SGB will be scheduled within 2 weeks of this visit, based on convenience and availability of the participant. Participants will be asked to complete a Hot Flash Related Daily Interference Scale and secondary outcome measures at this visit. They will complete a hot flash diary for at least 1 week. To qualify for study inclusion, participants must have ≥ 28 hot flashes per week or will be considered a screen failure and will be excluded.

Visit 2

Intervention

Participants will be NPO for 6 hours prior to the intervention and will arrange transportation home. At the time of the injection procedure, an angiocatheter will be placed in the hand/arm for peripheral intravenous access as a safety precaution. Participants will be positioned supine in cervical extension on a procedure table in the fluoroscopy suite of the NMH Pain Clinic (Lavin 1400). The anterior neck will be prepped with chlorhexidine and draped in the standard sterile manner.

A right-sided SGB will be performed. Using fluoroscopic guidance, the C6 vertebra will be identified and the skin overlying the tubercle will be anesthetized using 2 mL of 1% lidocaine. Using digital pressure to laterally retract the carotid artery, a 22 g 1.5-inch needle will be placed to make contact with the anterolateral portion of the C6 vertebra and then retracted 1-2 mm and secured; contrast material (iopamidol 1-2 mL) will be injected with fluoroscopic guidance to confirm contrast dye spread in the prevertebral fascial plane and to rule out intravascular or intrathecal dye spread. 0.5% bupivacaine (5 mL) will be injected and the needle will be removed.

Monitoring after SGB

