Nominal patient characteristics data will be summarized descriptively as number and percent of participants in each category. Ordinal and continuous patient data that are not approximately normally distributed will be summarized as median and interquartile range (IQR). Normally distributed continuous patient data will be presented as mean \pm SD.

STU#:00208657

Version 3.1

11/25/2019

Data required for the primary outcome variable, i.e., mean daily frequency of severe hot flashes in the study sample at 6 months after the intervention vs. the baseline daily frequency of hot flashes in the study sample, will be reported as the mean \pm SD if appropriate, or as the median (IQR) otherwise. The primary outcome data will be evaluated using a paired t-test if the data are approximately normally distributed, or using with the Wilcoxon matched pairs signed rank test if they are not. The mean difference and 95% CI will be calculated. The criterion for rejection of the null hypothesis (i.e. no change over the baseline to 6-month follow-up assessment of the mean weekly frequency of severe hot flashes) will be a two-tailed $p < 0.05$.

For AE analysis, safety and tolerability will be summarized descriptively by providing the frequency of adverse events by severity, type, and attribution.

Differences from baseline and associated 95% CIs will be calculated for planned analyses. Variables that are approximately normally distributed (e.g., hot flash frequency) will be summarized as mean \pm SD. These data at baseline, 1, 3, and 6 months will be compared using the one-way repeated measures analysis of variance with pairwise multiple comparison with baseline made using the Holm-Sidak method when appropriate.

The criterion for rejection of the null hypothesis for all of the secondary analyses will be a two-tailed $P < 0.05$, as this is an exploratory study.

With severe HF frequency selected as the primary outcome, $> 35\%$ reduction from baseline to 6 months will be considered to be clinically significant. However, as this is an exploratory study, a larger reduction was used for the power analysis presented above.

If this study shows meaningful treatment effects in this study population, we plan to further evaluate our hypotheses in a larger, randomized blinded sham controlled study.

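### Section 14 lets men be withdrawn for starting a hot-flash medication after a one-time block; the paired primary analysis may then lose probable non-responders, and Section 17 has no rule for them

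*Combined protocol and SAP*

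**What the plan says.** Section 14.0 says that participants "may be withdrawn from the research without their consent" and gives as its example "if they are non-compliant with providing outcome measures and/or if they begin using a medication known to have an effect on HF". Their status then becomes inactive. The same section contains a safeguard: "The reason(s) for discontinuation must be clearly documented on the appropriate CRF".

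The intervention is a single right-sided block at Visit 2 (Section 5.2). Daily diaries and weekly reminders are planned through 6 months (Section 5.2, Follow-Up; Schedule of Events, notes 11 and 12).

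The Study Summary sets the sample size at 14 men "needed to be evaluable both at baseline and 6 months for the primary outcome". In the Statistical Plan of Section 17.0, "The primary outcome data will be evaluated using a paired t-test if the data are approximately normally distributed"; otherwise the Wilcoxon signed rank test is used. Either test needs two values per man. A reduction of more than 35% is to be read as clinically significant. The rejection rule is separate: two-tailed p < 0.05.

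Section 17.0 gives no rule for newly started medication, no missing-data method and no sensitivity analysis. No planned analysis uses the recorded reason for discontinuation.

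**The concern.** Once the block has been given, no study treatment remains to stop. Withdrawal from the research therefore acts mainly on the data. One of the two named grounds, starting a medication that affects hot flashes, may itself be a result of the outcome: a man whose hot flashes did not improve has a reason to seek something else. If such men leave before the primary time point and the paired test uses those who remain, the analysed group has been selected partly on response.

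The trial has one arm, so no concurrent comparison would reveal this. At stake is the size of the reported reduction and how it reads against the >35% benchmark. The likely direction is overstatement, but only for men who start medication because relief was inadequate. Men who stop reporting may have done well or badly. Section 9.0 names drug classes, such as SSRIs, that a man may start for reasons unrelated to hot flashes.

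**Working it through.** **Inputs.** From Section 17.0, Power Analysis: baseline 46.0 severe hot flashes per week, SD1 43, SD2 21, correlation 0.8, a 52% reduction, about 20% attrition, up to 18 recruited. From Section 17.0, Statistical Plan: the >35% benchmark. From Section 2.0: a 52% fall with the block in women, "as compared to a 13% decrease in women in the sham control group who underwent an injection of saline".

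**The plan's own figures.** SD of change = √(43² + 21² − 2 × 0.8 × 43 × 21) = √845.2 = 29.07. With a difference of 23.9 per week, two-sided 0.05 and the noncentral t distribution, 14 pairs give 81.1% power. Correlation 0.7 gives SD 32.03 and N = 17. Attrition: 14 / 0.8 = 17.5, so 18. All three stated sizes reproduce.

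**Assumptions not in the documents.** 18 men are treated; k of them are removed before the primary time point; all have the same mean baseline; completers fall 52%; removed men fall r%.

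**Formulas.** All-treated fall = [52 × (18 − k) + r × k] / 18. Completer fall at which the all-treated fall is exactly 35% = (35 × 18 − r × k) / (18 − k).

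| k removed | All-treated fall, r = 0 | All-treated fall, r = 13 | Completer fall for 35% overall, r = 0 | Same, r = 13 |
|---|---|---|---|---|
| 1 | 49.1% | 49.8% | 37.1% | 36.3% |
| 2 | 46.2% | 47.7% | 39.4% | 37.8% |
| 3 | 43.3% | 45.5% | 42.0% | 39.4% |
| 4 | 40.4% | 43.3% | 45.0% | 41.3% |

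For example, k = 4 and r = 0 gives 52 × 14 / 18 = 40.4%, and 35 × 18 / 14 = 45.0%. If removed men responded like completers (r = 52), the shift is zero. The 13% column only shows how the answer moves; that figure comes from women.

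**Which rows are plausible.** Four removed men would use the whole attrition allowance (4/18 = 22%) on this one cause, so 1 or 2 is more realistic. Eighteen treated is itself a ceiling. Section 11.0 uses 18 for the "Maximum Number to be Consented or Reviewed/Collected/Screened", and under Section 5.2 a man below the diary threshold "will be considered a screen failure and will be excluded". With 16 treated, r = 0 and 1 or 2 removed, the all-treated fall is 52 × 15/16 = 48.8% or 52 × 14/16 = 45.5%.

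**Against sampling error.** The 95% half-width for the mean change is t × 29.07 / √n. For n = 17 it is 2.120 × 29.07 / 4.123 = 14.9 per week, or 32.5% of 46. For n = 16 it is 2.131 × 29.07 / 4 = 15.5 per week, or 33.7% of 46. The corresponding shifts with 1 or 2 removed men unchanged are 2.9 and 5.8 percentage points.

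**The case against.** The strongest reply is that the plan never says withdrawn men's data are discarded. Withdrawal is discretionary, the text offers examples rather than a rule, reasons are recorded, and daily diaries up to withdrawal already exist. This stands: omission is inferred from the paired tests and the evaluable-at-both-times definition. It also depends on timing. Section 3.0 puts the primary at 3 months, while the Study Summary and Section 17.0 put it at 6 months. A man withdrawn at month 4 would contribute to the first and not the second.

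The size can also be challenged. At the planned 52%, every all-treated value above stays over 35%, and the realistic shift is small beside a half-width of about 32 to 34% of baseline. The documents give no rate of new medication starts, and some men may already be taking the allowed drugs at a stable dose. All of this stands, and it limits the point to results near 35%.

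A reader might infer more than the text supports:

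- That the completer change at the primary time point is the only effect estimate. Sections 3.0 and 17.0 also plan comparisons with baseline at other visits, and some men withdrawn later would have those earlier values.
- That an inflated effect size will be carried into the next trial. Section 17.0 speaks of carrying forward hot flash frequency and variability, not expressly the effect.
- That >35% is a go/no-go rule. It is a reading of clinical significance in a self-described exploratory study.
- That the sample size is wrong. It reproduces.

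What the reply does not remove is that no text says collection continues after withdrawal, and Section 17.0 does not say how these men are handled.

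**Conclusion.** The point holds in conditional form. As written, Section 14.0 can end outcome collection for men whose reason for leaving is a poor response, and Section 17.0 has no analysis that would show it. The overstatement is probable only for men who start a medication because relief was inadequate; otherwise the direction is unknown.

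Under the assumptions shown, with removed men unchanged, a 52% completer result stands for 49.1% or 46.2% among all treated when 1 or 2 men are removed, and for 40.4% when 4 are. In the four-man case, a completer result above 35% but below 45.0% would exceed the benchmark while the all-treated result would not. No response rate for withdrawn men is given, so these figures illustrate the effect and do not estimate it. The documents do not support saying that the reported reduction will be biased. This is a cheap improvement to the plan and does not invalidate the trial.

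**What to change.** 1. **Section 14.0.** State that starting a medication that affects hot flashes, or missing reports, does not by itself end data collection. Diaries and questionnaires continue to 6 months unless the man declines. Record the medication, its start date and the reason. This concerns data collection only, not clinical care.

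2. **Section 17.0.** Keep the paired primary test. State that values after a newly started medication are not counted as response to the block. Add one sensitivity analysis of all treated men:
   - a man who starts such a medication contributes his last complete diary week before it and, as a conservative bound, his baseline value;
   - a man with no primary value for any other reason is set to baseline.

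   Report the percent reduction from this analysis beside the completer result, both against >35%, with the number withdrawn by recorded reason. Do not report its p-value, because filled-in values understate variability.

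3. **Time point.** Apply this at whichever primary time point is kept once Section 3.0 (3 months) is reconciled with the Study Summary and Section 17.0 (6 months).

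**Cost.** Some protocol and analysis wording and slightly more analysis work; the diaries and reminders are already planned. The reported reduction may come out smaller, and men who never resume reporting will still lack observed values.
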